Research in cortical excitability or cortical plasticity modulations highlighted the significance of such processes in the potential enhancement of motor recovery after cerebrovascular stroke. The modules involved in cortical reorganization post stroke can potentiate the results of clinical rehabilitation of various motor impairments in stroke patients. Non-invasive brain stimulation with inhibitory repetitive transcranial magnetic stimulation (rTMS) of the contralesional hemisphere may aid in relieving a post-stroke interhemispheric excitability imbalance, which could improve functional recovery (**Van et al, 2017**) Abnormal cortical excitability and interhemispheric imbalance in stroke patients assumes that, the increased excitability of the contralesional hemisphere applies excessive interhemispheric inhibition onto ipsilesional cortical hemisphere . This excessive imbalanced inhibition impede the neuroplasticity in these areas and limit the gains in motor recovery that can be achieved through rehabilitation (**Boddington & Reynolds 2017**).

Null Hypothesis:

- There is no significant effect of using contralesional low frequency repetitive transcranial magnetic stimulation (LF-rTMS) on cortical excitability and consequently on the motor performance of the affected upper limb in stroke patients.
- There is no change in the sessional values of cortical excitability in response to contralesional low frequency repetitive transcranial magnetic stimulation (LF-rTMS) thus the recommended minimum and maximum number of LF-rTMS sessions that can show significant changes in cortical excitability cannot be determined in stroke patients.

Delimitations:

This study was delaminated to:-

- Forty hemiparetic stroke patients of both genders who met all the inclusion criteria were recruited in this study from outpatient clinic, Faculty of Physical Therapy and outpatient clinic in the Neurology department, Faculty of Medicine, Cairo University.
- Their age ranged from 50 and 65 years
- All patients experienced single ischemic stroke for at least three months but not exceeded for six months.

- All patients were referred from a neurologist and the diagnosis was confirmed with non-contrast computed tomographic (CT) or magnetic resonance imaging (MRI) scans of the brain.

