- The selected patients were randomly assigned into two equal groups (control group (GA) and study group (GB)), The randomization was done by random generator using permuted blocks of different sizes(Randomized Controlled Trial).
- All patients were selected with mild to moderate motor impairment verified according to the national istitutes of health stroke scale (NIHSS) (score 1-15) and modified ashworth scale (MAS) (1 or 1+).
- Fugl-Myer upper extremity assessment scale (FMA-UE) and hand grip dynamometer were used to assess the upper limb motor function for each patient in both groups (before and after treatment).
- Single pulse TMS was used to assess cortical excitability represented in measuring the active motor threshold from the contralesional (CAMT) and the ipsilesional (IAMT) primary motor “hot spot” for each patient in both groups (before and after treatment).
- Single pulse TMS was used to assess the sequential change in cortical excitability represented by the sessional measurement of (CAMT) and (IAMT) for all patients in both groups.
- Patients participated in the study were not informed whether they are in the Control group(GA) or in the Study group(GB) (Single blind study).
- The treatment sessions for all patients in both groups was conducted daily, five times per week for two consecutive weeks.
 - The control group (GA) were treated by a conventional physical therapy upper limb rehabilitation protocol (**Lie et al,2015**).

- The study group (GB) were treated with the conventional physical therapy upper limb rehabilitation protocol in addition to the contralesional low frequency repetitive transcranial magnetic stimulation (LF-rTMS).

Limitations:

An Effort was made to minimize the effect of the possible limitations which are:

1. The psycho-physiological status of the patients; all the patients were interested and motivated during all the sessions.
2. The transportation of all patients from the Outpatient clinic, Faculty of Physical Therapy, Cairo University was comfortable and without any effort or extra load on the patient as much as possible.
3. Each patient was assessed using single pulse TMS at the neurophysiology lab at Kasr El Aini, teaching Hospital, Cairo University, at a time suitable for each patient and without any list of waiting as much as possible.

Basic assumption:

It was assumed that:

- The sample of this study were carefully selected to represent all the subacute stroke population.

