- Patient's motivation & cooperation were the same throughout the assessment and treatment procedures for each patient.

- All other factors which may influence the outcomes such as noise, distraction....etc during the assessment and treatment sessions were controlled.
- All risk factors of stroke would be controlled to avoid any recurrent stroke or instability of their medical state like blood pressure, glucose and cholesterol level that was achieved with their physicians.

Data Analysis and Statistical Design:

A- Descriptive statistics:

The mean value and standard deviations for upper limb motor function findings represented in **Fugl-Myer Upper Extremity Scale (FMA-UE)**, **Hand grip dynamometer** and Findings of cortical excitability represented in **Contralesional Active Motor Threshold (cAMT) and Ipsilesional Active Motor Threshold (iAMT)** obtained from MagstimRapid² stimulator system were compared for both groups (Control group (GA) and Study group (GB)).

B- Inferential statistics:

- **Student t Test** was used to compare different numerical variables represented in mean values and standard deviations of the patients **chronological features as Age (in years) and duration since onset of stroke (in months)** between both groups ((GA) and (GB)).
- **Student t Test** for independent samples test was also used to compare different numerical variables represented in mean values and standard deviations that were obtained from MagstimRapid2 stimulator system (

cAMT , iAMT) for cortical excitability and upper limb motor function findings (Fugl-Myer assessment- Upper Extremity (FMA-UE), Hand grip dynamometer) between both groups ((GA) and (GB)) (Pre treatment findings).

- **Chi-square (χ^2) Test** was performed to compare the **categorical data** of the patients' main features as gender, smoking history, within and between groups (control group (GA) and study group (GB)). **Fisher's Exact Test** was used instead when the expected frequency is less than 5.
- **Paired t Test** for independent samples test was used to compare the post to pretreatment change between both groups, represented in the mean values and standard deviations obtained for the recorded post to pretreatment difference in cortical excitability (cAMT , iAMT) and upper limb motor function findings ((FMA-UE), Hand grip dynamometer) .

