- The mean values of the **Sequential rate of change in cAMT and iAMT** findings over the 10 therapeutic sessions were assessed by comparing the CAMT and the IAMT mean values of each session in relation to the previous session findings for each patient in both groups
- **Paired t Test** for independent samples test was used to compare the mean sessional values (sequential change) and the mean difference in the sessional rate of change of the **cortical excitability findings** represented by cAMT and iAMT between group control group (GA) and study group (GB).
- The alpha point of 0.05 was used as a level of statistical significance (when P = 0.05 is usually classed as “significant”, P = 0.01 as “highly significant”, and P = 0.001 as “very highly significant”) (**Betty and Jonathan, 2003**).

- All statistical calculations were done using computer program IBM SPSS (Statistical Package for the Social Science; IBM Corp, Armonk, NY, USA) release 22 for Microsoft Windows.

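### Both treatment comparisons name a paired t test for independent samples, which is a contradiction; correct the label and confirm which test was run

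*Combined protocol and SAP*

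**What the plan says.** All of this is in the combined protocol and SAP. Under Data Analysis and Statistical Design, B- Inferential statistics, three places matter.

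- **Change from before to after treatment.** "Paired t Test for independent samples test was used to compare the post to pretreatment change between both groups". The variable is "the recorded post to pretreatment difference in cortical excitability" (cAMT and iAMT), and likewise in FMA-UE and hand grip.
- **Session values.** "Paired t Test for independent samples test was used to compare the mean sessional values (sequential change") and the difference in the sessional rate of change, "represented by cAMT and iAMT between group control group (GA) and study group (GB").
- **Session to session.** The bullet before that one describes "comparing the CAMT and the IAMT mean values of each session in relation to the previous session findings for each patient in both groups". It names no test.

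The pretreatment bullet in the same section has a coherent label: "Student t Test for independent samples test was also used to compare different numerical variables".

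Delimitations gives the design: forty patients, and "The selected patients were randomly assigned into two equal groups (control group (GA) and study group (GB"). No matching or crossover is described. The second null hypothesis rests on the session analysis: "There is no change in the sessional values of cortical excitability in response to contralesional low frequency repetitive transcranial magnetic stimulation (LF-rTMS").

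**The concern.** A paired t test needs observations that are linked one to one; an independent-samples t test needs observations that are not. The label asks for both. The groups are separately randomised patients, so there are no natural pairs between GA and GB.

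The slip falls where it matters most. These two bullets are the only ones that name a test for a comparison between groups after treatment starts, and together they cover all four outcomes. A reader cannot tell from the text which of these was done:

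1. an independent-samples test on each patient's value, which is valid;
2. patients of GA paired with patients of GB, so that the p-value depends on the order of the rows;
3. paired pre-post tests within each group only, so that the difference between groups is never tested;
4. for the session data, the session means of GA paired with those of GB, which leaves lasting differences between patients out of the error term.

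**Working it through.** **Inputs.** From the documents: 40 patients in two equal groups, so n = 20 per group; 10 sessions; alpha 0.05. The plan gives no sidedness, effect size, SD or correlation. I take two-sided tests and show ranges for the rest. The plan states no figure that could be reproduced.

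**Form 1: independent-samples test on change.** df = 20 + 20 − 2 = 38, critical t = 2.024. There is no numerical error.

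**Form 2: patients paired across groups in arbitrary order.** df = 20 − 1 = 19, critical t = 2.093. The noncentrality is d·√(n/2) = d·√10 for both tests, so only the degrees of freedom differ.

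| Assumed d | Noncentrality | Power, independent | Power, arbitrary pairs |
|---|---|---|---|
| 0.5 | 1.58 | 33.8% | 32.4% |
| 0.8 | 2.53 | 69.3% | 67.0% |
| 1.2 | 3.79 | 95.9% | 94.9% |

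Type I error stays near 5% (5.2% for both tests in 100,000 simulated trials). The two tests reach different decisions in 2% of trials at d = 0, 7% at 0.5 and 0.8, and 2% at 1.2. To isolate the effect of row order, normal data sets were fixed at a given independent p and re-paired at random (800 data sets, 400 pairings each):

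| Independent p | Paired p, central 95% of pairings | Crossing 0.05 |
|---|---|---|
| 0.01 | 0.002 to 0.035 | under 0.1% rise above |
| 0.04 | 0.011 to 0.092 | 45% rise above |
| 0.10 | 0.037 to 0.175 | 6% fall to or below |

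**Form 3: within-group pre-post tests only.** Suppose the true standardised change c is the same in both groups. Let p be the power of one paired test (df 19, noncentrality c·√20). Exactly one group is significant with probability 2p(1 − p).

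| c | p | 2p(1 − p) |
|---|---|---|
| 0.1 | 0.071 | 13% |
| 0.2 | 0.136 | 23% |
| 0.3 | 0.247 | 37% |
| 0.5 | 0.565 | 49% |
| 0.75 | 0.889 | 20% |
| 1.0 | 0.989 | 2% |

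In half of these cases the significant group is GB. That pattern could be read as a treatment effect although there is none.

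**Form 4: ten session means paired across groups.** Let r be a constant correlation between sessions within a patient. The mean of the ten differences has variance 2rσ²/n + 2(1 − r)σ²/(10n). The paired test estimates only the second term, because a lasting group difference due to chance is the same at every session. The ratio of the true to the estimated variance is 1 + 10r/(1 − r). Under no treatment effect the statistic is therefore a t with 9 df multiplied by √(1 + 10r/(1 − r)). The critical value is 2.262, and the type I error is P(|t₉| > 2.262/multiplier).

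| r | Multiplier | 2.262/multiplier | Type I error |
|---|---|---|---|
| 0.1 | 1.453 | 1.557 | 15.4% |
| 0.3 | 2.299 | 0.984 | 35.1% |
| 0.5 | 3.317 | 0.682 | 51.2% |
| 0.7 | 4.933 | 0.459 | 65.7% |
| 0.9 | 9.539 | 0.237 | 81.8% |

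A patient-level simulation (10,000 trials) gave 34.2%, 50.9%, 65.2% and 82.2% at r = 0.3, 0.5, 0.7 and 0.9. An independent-samples test on each patient's session mean gave 4.6% to 5.1% in the same trials. With first-order autoregressive correlation of 0.3, 0.5, 0.7 and 0.9 (40,000 trials) the session-paired error was 13.5%, 25.0%, 41.0% and 66.9%.

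Pairing the nine session-to-session changes behaves differently, because lasting differences between patients cancel. The error was under 0.1% with constant correlation, 0.01% to 2.2% autoregressive and 4.7% for a random walk. It was inflated only when patients' slopes differed widely: 2.4% at an assumed slope SD of 0.2 per session and 25.9% at 0.5 (constant correlation 0.7, total SD 1 at session 1).

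**The case against.** The strongest reply is that this is a repeated slip of one word. The change bullet says independent samples, compares the two groups and analyses a recorded difference. That describes an independent-samples t test on change, which is valid, and it covers all four outcomes. This stands as the likeliest reading of that bullet, but the documents do not confirm it.

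The other forms can also be played down. Arbitrary pairing costs 1.0 to 2.3 percentage points of power, leaves type I error nominal and matters mainly near p = 0.05. That is correct. Within-group tests alone would contradict both sentences, which speak of comparing the groups; so Form 3 is possible but not what the text says.

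For the session data, one pooled p-value over ten session means could not show at which session an effect appears or levels off, which is a stated purpose of the study. Thresholds were measured at each session for every patient, so a session-by-session comparison was feasible and fits the aim better. This makes Form 4 a worst case. It does not remove the ambiguity: the sentence speaks of comparing mean sessional values, and the neighbouring within-patient comparison, where a paired test could be proper, names no test.

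The objection therefore limits how much harm to expect. It does not show which test was run.

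**Conclusion.** The concern holds. As written, the named test for both treatment comparisons contradicts itself, and a paired test does not fit two unmatched randomised groups. The plan is not shown to have produced wrong results. For the post-minus-pre change, the likeliest reading carries no numerical error. For the session values, the meaning is open, and the worst reading gives false-positive rates of 15% to 82% at constant within-patient correlations of 0.1 to 0.9. All effect sizes, correlations and slope SDs behind these figures are assumptions, since the documents give none. The point must be fixed because no treatment p-value can be confirmed as valid until it is, and settling it costs almost nothing.

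**What to change.** - **Change bullet:** replace the label with Student t test for independent samples, the term already used for the pretreatment comparison, applied to each patient's post-minus-pre change, GA against GB. Welch's version is optional.
- **Session bullet, between groups:** use an independent-samples comparison at each session with the patient as the unit, or one repeated-measures model over the 10 sessions with group, session and their interaction. Either is sound. Do not pair session means across groups.
- **Session-to-session bullet, within patients:** name the test. A paired test is proper here if it is labelled as within-group and no treatment conclusion rests on it.
- **Confirmation:** state, for each comparison, which test was actually run.

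The cost is a wording change in two bullets and a test name in a third. A re-run in the same software is needed only if patients were paired across groups, session means were paired across groups, or only within-group tests were done. No new data are needed.

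### The between-group comparison of all four pre/post outcomes uses unadjusted change scores; adjusting for the pre-treatment value would usually be more precise with 20 patients per arm (efficiency, not bias)

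*Combined protocol and SAP*

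**What the plan says.** The Delimitations section gives the design. "Forty hemiparetic stroke patients of both genders who met all the inclusion criteria were recruited", and "The selected patients were randomly assigned into two equal groups", which makes 20 per arm. All four outcomes are measured at both ends of treatment:

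- FMA-UE and grip: the scale and "hand grip dynamometer were used to assess the upper limb motor function for each patient in both groups (before and after treatment".
- Motor thresholds: "Single pulse TMS was used to assess cortical excitability represented in measuring the active motor threshold from the contralesional (CAMT) and the ipsilesional (IAMT") hot spot, also before and after treatment in both groups.

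Data Analysis and Statistical Design, part B (Inferential statistics), uses the pre-treatment values in two ways. They are tested for a difference between the arms at entry, the compared variables ending with "Hand grip dynamometer) between both groups ((GA) and (GB)) (Pre treatment findings"). They are also subtracted from the post values: a paired t test "for independent samples test was used to compare the post to pretreatment change between both groups", applied to "the mean values and standard deviations obtained for the recorded post to pretreatment difference in cortical excitability" and in the two motor function measures.

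No ANCOVA, regression or other baseline adjustment appears anywhere. The documents also give no SD, pre-post correlation, target effect or power.

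**The concern.** Subtracting the pre value is the same as adjusting for it with the slope fixed at 1. The slope that minimises the variance is the pre-post correlation multiplied by SDpost/SDpre, and it equals 1 only by coincidence. When it differs from 1, the change score carries avoidable noise. Given a chance baseline imbalance, the estimate moves by (1 − slope) times that imbalance. This movement is the source of the extra variance, not a second harm.

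At stake is the precision of four treatment comparisons in a 40-patient trial. Validity is not at stake.

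The test name contradicts itself, since a t test cannot be both paired and for independent samples. I read it as an unpaired t test on change, because the sentence says the comparison is between the groups. That reading is an assumption. On either reading there is no baseline adjustment.

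**Working it through.** The plan states no power or precision figure, so there is nothing to reproduce.

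**Inputs from the documents.** N = 40 in two equal groups, so n = 20 per arm; alpha 0.05. Sidedness is not stated, and two-sided is assumed.

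**Assumed inputs.** Pre-post correlation ρ, SD ratio k = SDpost/SDpre (with SDpre = 1), and for power a treatment effect of 0.8 SD.

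**Formulas**

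- Change-score variance per patient: 1 + k² − 2ρk.
- ANCOVA residual variance: k²(1 − ρ²), multiplied by 1 + 1/(N − 4) = 1 + 1/36 = 1.028 for the cost of estimating the slope.
- Ratio = ANCOVA variance / change-score variance. With k = 1 this reduces to (1 + ρ)/2 × 1.028.
- Change-score patients per arm needed to match ANCOVA on 20 per arm: 20 / ratio.
- Power: noncentral t, with 38 degrees of freedom for change and 37 for ANCOVA.

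Example at ρ = 0.5, k = 1: change variance 1 + 1 − 1 = 1.00; ANCOVA variance 0.75 × 1.028 = 0.771; ratio 0.771; 20/0.771 ≈ 26.

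**Equal SDs (k = 1)**

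| ρ | Variance ratio | Net saving | Equivalent n per arm | Power for 0.8 SD, change vs ANCOVA |
|---|---|---|---|---|
| 0.3 | 0.668 | 33% | 30 | 55% vs 72% |
| 0.5 | 0.771 | 23% | 26 | 69% vs 80% |
| 0.7 | 0.874 | 13% | 23 | 89% vs 93% |
| 0.8 | 0.925 | 7% | 22 | 97% vs 98% |
| 0.9 | 0.976 | 2% | 20 | both above 99.9% |
| 0.95 | 1.002 | nil | 20 | both above 99.9% |

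Break-even is at ρ = 2/1.028 − 1 ≈ 0.946.

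**Unequal SDs: net saving from ANCOVA**

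| k | ρ = 0.5 | ρ = 0.7 | ρ = 0.8 | ρ = 0.9 |
|---|---|---|---|---|
| 0.8 | 41% | 35% | 34% | 37% |
| 0.9 | 31% | 23% | 19% | 17% |
| 1.1 | 16% | 5% | 0.5% | −3% |
| 1.25 | 8% | −1% | −3% | 2% |

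The worst case is a slope of exactly 1 (k = 1.25, ρ = 0.8), where ANCOVA loses the full 1/36, about 3%.

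**Conditional shift.** The standard error of the baseline difference is √(2/20) = 0.316 SD. With k = 1, an imbalance of that size shifts the change-score estimate by (1 − ρ) × 0.316: 0.16 SD at ρ = 0.5, 0.09 at 0.7 and 0.03 at 0.9.

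**Simulation check.** With 100,000 trials per setting, the variance ratios were 0.770, 0.876, 0.977 and 1.003 at ρ = 0.5, 0.7, 0.9 and 0.95 (k = 1), and 1.028 at ρ = 0.8, k = 1.25. The mean error of the change-score estimate was within 0.003 SD of zero. Type I error at ρ = 0.5 was 5.0% for change and 4.9% for ANCOVA.

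**The case against.** A change-score comparison is a legitimate analysis that can be specified in advance, and the gain from replacing it cannot be established from these documents. Across the assumed values above, the net saving runs from 41% to −3%. The large power differences appear only at correlations of 0.3 to 0.5 and rest on an assumed 0.8 SD effect. Measurements two weeks apart on the same patients and instruments, at least three months after stroke, may well correlate highly. A post SD only 10% larger than the pre SD removes nearly all the gain at a correlation of 0.8. At k = 1.25 and ρ = 0.7, power is 78.1% for change and 77.7% for ANCOVA. The analysis section is written in the past tense, so the results may already be known. The contradictory test name also has to be settled first: if a paired test was really run, these efficiency figures do not describe it.

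Most of this stands and limits how much weight the point can carry. It does not remove the point, because the expected loss from adjusting is bounded at about 3% while the possible gain is several times larger, so the choice does not require knowing the correlation. High correlation alone does not settle the matter either: at ρ = 0.9 with k = 0.8 the saving is still 37%. The past tense determines how the adjusted analysis should be labelled. The test name must be corrected anyway, and the model can be specified in the same edit.

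**Conclusion.** The concern holds as a matter of efficiency. The planned comparison is unbiased with the correct type I error, but it leaves unused information already held on every patient. The loss is material at low to moderate correlation (23% of variance at 0.5 and 13% at 0.7 with equal SDs). It is negligible at about 0.9 or above with similar SDs, and absent when the slope is near 1. These sizes rest on assumed correlations and SDs, and on reading the test as an unpaired t test on change. The change should be made, but no result is invalid without it. The pre-treatment significance tests alter no treatment comparison and are a minor reporting matter.

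**What to change.** In part B of Data Analysis and Statistical Design, replace the contradictorily named t test on change with an ANCOVA for each of cAMT, iAMT, FMA-UE and hand grip: post value = group + that outcome's own pre value. Report the adjusted GB − GA difference with its 95% confidence interval. State which t test the present wording meant.

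If the data have already been examined, label the ANCOVA as a revised analysis and report it beside the planned change-score comparison, so that neither result is selected after the fact. As a minor point, present baseline characteristics descriptively, without significance tests.

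No new data or visits are needed, and the named software can fit the model ("All statistical calculations were done using computer program IBM SPSS"). The statistical cost is one degree of freedom and at most about 3% of variance.

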Low-frequency repetitive transcranial magnetic stimulation (LF-rTMS) of the contralesional hemisphere is a safe procedure that suppresses local cortical activity of the non-affected cerebral cortex (**Li et al, 2016**). The primary motor cortex (M1) forms a main part of the motor cortices and contributes to the high order control of motor recovery of the hemiparetic upper limbs in stroke patients. It was assumed that the induced inhibitory effect of LF-rTMS on the non-lesional hemisphere can cause direct increase in the neural activation of the lesional hemisphere which can consequently regain the cortical interhemispheric balance and eventually can produce functional improvement in post-stroke patients with upper limb hemiparesis (**Blesneag et al,2015, Du et al, 2018**).

Statement of the Problem:

- Is there a significant effect of the contralesional low frequency repetitive transcranial magnetic stimulation (LF-rTMS) on cortical excitability modulation and consequently on the upper limb motor performance in stroke patients?
- The recommended minimum number of contralesional low frequency repetitive transcranial magnetic stimulation (LF-rTMS) sessions that can induce significant cortical excitability changes in relation to the conventional therapeutic physical therapy interventions in stroke patients?
- The recommended maximum number of contralesional low frequency repetitive transcranial magnetic stimulation (LF-rTMS) sessions that can induce significant cortical excitability changes before reaching a plateau in relation to the conventional therapeutic physical therapy interventions in stroke patients?

Purpose of the study:

- To assess and analyze the effect of contralesional low frequency repetitive transcranial magnetic stimulation (LF-rTMS) on cortical excitability and consequently its impact on the upper limb motor performance in stroke patients.
- To determine the recommended minimum and maximum number of contralesional low frequency repetitive transcranial magnetic stimulation sessions (LF-rTMS) in conjunction with the conventional physical therapy rehabilitation program that can induce significant impact on cortical excitability by analyzing the sequential rate of change in cortical excitability in response to contralesional (Lf-rTMS) stimulation in stroke patients.

Significance of the study

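### The plan promises a minimum and maximum number of sessions but gives no rule for either; significance, the criterion it points to, gives a minimum that moves with sample size and cannot show a plateau

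*Combined protocol and SAP*

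**What the plan says.** In the combined protocol and SAP, Purpose of the study sets the aim: "To determine the recommended minimum and maximum number of contralesional low frequency repetitive transcranial magnetic stimulation sessions (LF-rTMS"), to be reached by analysing the sequential rate of change in cortical excitability. Statement of the Problem ties the maximum to "significant cortical excitability changes before reaching a plateau in relation to the conventional therapeutic physical therapy interventions". The second null hypothesis treats the two numbers as following from significance: "thus the recommended minimum and maximum number of LF-rTMS sessions that can show significant changes in cortical excitability cannot be determined in stroke patients".

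The design is in Delimitations: "Forty hemiparetic stroke patients of both genders who met all the inclusion criteria were recruited"; "The selected patients were randomly assigned into two equal groups"; treatment was "conducted daily, five times per week for two consecutive weeks"; and the sequential change in excitability is "represented by the sessional measurement of (CAMT) and (IAMT) for all patients in both groups".

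The only supporting analysis is in Data Analysis and Statistical Design, B- Inferential statistics. One item describes "comparing the CAMT and the IAMT mean values of each session in relation to the previous session findings for each patient in both groups" and names no test. The next compares session values and session-to-session change of cAMT and iAMT between the groups, with a t test named as both paired and for independent samples. Alpha is 0.05, with no multiplicity control. The post-minus-pre comparison in the same section carries the same test name.

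**The concern.** The number of sessions is one of two stated purposes, and readers would take the answer as a recommendation. Yet the text does not say which comparison, which threshold (cAMT or iAMT) or what size of change fixes the minimum, and it does not define a plateau. Two analysts could follow it exactly and report different numbers.

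If significance is the intended criterion, two problems follow. The first significant session depends on how many patients were studied as well as on the treatment. And a non-significant change from one session to the next is the expected result at this sample size even while the effect is still growing, so it is not evidence of a plateau.

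**Working it through.** The documents contain no sample-size calculation, SD, correlation or effect size, so there is no planned figure to reproduce.

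**From the documents:** 40 patients in two equal groups, so 20 per arm; 5 sessions a week for 2 weeks, so 10 sessions; alpha 0.05 per test (two-sided assumed).

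**Assumed:** values scaled to SD 1; between-session correlation 0.7, 0.8 or 0.9, either constant or serial (AR(1)); an effect rising linearly to 0.91 SD at session 10, or 0.091 SD per session. That total gives 80% power at session 10: noncentrality 0.91 × √(20/2) = 2.88 on 38 df.

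1. **Minimum as the first significant session.** A group difference is significant when it exceeds t × √(2/n). Dividing by 0.091 gives the session at which the true difference reaches that limit:
   - n = 20: 2.024 × √(2/20) = 0.640; 0.640/0.091 = 7.0
   - n = 40: 1.991 × √(2/40) = 0.445; 0.445/0.091 = 4.9
   - n = 80: 1.975 × √(2/80) = 0.312; 0.312/0.091 = 3.4
   - n = 160: 1.967 × √(2/160) = 0.220; 0.220/0.091 = 2.4

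   Simulation at correlation 0.8 (2,000 trials per n) gives median first significant sessions of 7, 5, 4 and 3 under constant correlation and 6, 5, 4 and 3 under serial correlation. The true curve is the same throughout.

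2. **Power of one step.** The SD of a session-to-session change is √(2(1 − ρ)), which is 0.632 at ρ = 0.8. The standardised step is 0.091/0.632 = 0.144, the noncentrality 0.144 × √10 = 0.455, and the power 7.3% (6.5% at ρ = 0.7, 9.6% at ρ = 0.9). A single step carrying half the total effect (0.455/0.632 = 0.719) has 60% power (44% and 88%).

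3. **Plateau from non-significant steps.** These are simulations with 20 per arm, nine steps (sessions 2 to 10) and correlations 0.7-0.9 of both kinds. With a steady rise and no plateau, no step is significant in about 38-55% of trials. With a true plateau at session 5 (0.91 SD reached at session 5, flat afterwards), the last significant step is session 5 in about 8-19%.

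4. **False signals with no effect, one threshold.** At least one session value is significant in 13-30% of trials, and at least one step in 33-37%.

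5. **Counting steps.** The plan does not say whether the sessional AMT is taken before or after stimulation. If session 1 is also compared with the pre-treatment value there are ten steps. A ten-step simulation (total 1.0 SD, constant correlation 0.5-0.9, steady rise) gives no significant step in 31-54% of trials; the last significant step falls before session 10, or no step is significant, in 90-93%. The conclusion is the same.

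6. **Range of observation.** All patients are scheduled for 10 sessions, so a plateau after session 10 cannot be observed.

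**The case against.** The strongest reply is that the plan does imply a minimum. It asks for the fewest sessions giving a significant change relative to conventional therapy, and it tests session values between groups; the first significant session is a natural reading. That stands. A reader might infer that the plan can yield no minimum at all, but the documents do not support this: the number exists and is a poor estimate. The stronger criticism applies to the plateau and the maximum.

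A reader might also pool every session-wise test, (10 values + 9 steps) × 2 thresholds = 38, and quote a 58-76% chance of a false positive. No plausible rule combines them all: a minimum would come from session values and a maximum from steps. The per-threshold figures in the working are the relevant ones.

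Nor is the post-minus-pre comparison undermined. It does not depend on the session-wise tests, and only its contradictory test name needs correcting.

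Finally, it can be said that more elaborate remedies do poorly with 20 per arm. That also stands. A joint test over all ten sessions at 0.025 has about 98% power for the linear effect under constant correlation 0.8 but about 24% under serial correlation 0.8, where a single baseline-adjusted session-10 comparison at the same level has 71%. Such a test, or a bootstrapped break-point, is therefore optional.

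**Conclusion.** The concern holds as a should-fix. That no rule links the session-wise results to a minimum, a maximum or a plateau can be read from the text and needs no assumption. The size of the harm is conditional on significance being the criterion, which the documents point to without writing it as a rule, and on the assumed correlations and effect. Within the ranges tried the direction did not change: the minimum tracks sample size, and a plateau read from non-significant steps is usually wrong. The first purpose, served by the post-minus-pre comparison, is not affected beyond the test name.

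**What to change.** 1. In B- Inferential statistics, name the independent-samples test for every between-group comparison, both post-minus-pre and session-wise, and delete the paired label there.
2. State whether the sessional AMT is measured before or after stimulation, and so whether session 1 is distinct from the pre-treatment value.
3. For cAMT and iAMT, report the baseline-adjusted group difference at every post-baseline session from one repeated-measures model that allows for serial correlation, with simultaneous 95% CIs. Show session-to-session changes descriptively only.
4. Do not infer a plateau or a maximum from p>0.05. Label any session-number statement exploratory and give its uncertainty. Where the intervals do not support a number, report that no minimum or maximum was identified within 10 sessions.
5. Name a minimum only against an AMT margin that the sponsor justifies. The document is written in the past tense, so disclose it if the margin was set after the data were seen.

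The cost is SAP wording and one model per threshold on data already specified for collection; check that the named software release offers the chosen covariance structure. The downside is wider intervals. With 20 per arm, correlation 0.8, the linear 0.91 SD effect and a purely illustrative 0.5 SD margin, a simultaneous-interval rule names a minimum in about 33% of trials (constant correlation) or 10% (serial). The trial may be unable to name a minimum or a maximum.
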